Coronary Computed Tomography Angiogram (CCTA) is a non-invasive imaging modality that has high sensitivity and negative predictive value for the detection of coronary artery disease (CAD). The main limitations of CCTA are its poor specificity and positive predictive value, as well as its inherent lack of physiologically relevant data on hemodynamic significance of coronary stenosis, a data that is provided either by non-invasive stress tests such as myocardial perfusion imaging (MPI) or invasively by measurement of the Fractional Flow Reserve (FFR). Recent advances in computational fluid dynamic techniques applied to standard CCTA are now emerging as powerful tools for virtual measurement of FFR from CCTA imaging (CT-FFR). These techniques correlate well with invasively measured FFR [1-4]. The primary purpose of this study is to evaluate the incremental benefit CT-FFR as compared to CCTA in triaging chest pain patients in outpatient settings who are found to have obstructive CAD upon CCTA (> 30% stenosis). Invasive FFR and short term clinical outcomes (90 days) will be correlated with each diagnostic modality in order to evaluate positive and negative predictive value of each when used incrementally with CCTA.

Patients will undergo a CCTA, as part of routine care. If the patient consents to participate in the study and is found to have coronary stenosis of 30% to 100%, based on the cardiologist's reading, the CCTA study will be sent to HeartFlow, a vendor that will provide a computerized FFR reading, based on the CCTA study. If the noninvasive FFR diagnosis indicates obstructive disease, the patient will undergo cardiac catheterization with invasive FFR.

As CCTA utilization increases, the need to train additional imaging specialists will increase. This study will assess the capability of FFR-CT to enhance performance on both negative and positive predictive value for less experienced readers by providing feedback based on CT-FFR evaluation. CCTA readers will be grouped in two categories: those with more than 10 years reading experience and those with less than 10 years reading experience. Each CCTA will be read by a less experienced and a more experienced reader. Results from each reader will be correlated with each other and with the CT-FFR and invasive FFR results.

3 Introduction

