3.4 Clinical Data to Date

From 1/1/2009 to 3/31/2015 our team introduced and operated a CCTA Chest Pain triage program for low to intermediate risk patients at Stony Brook University Hospital ED and non-emergency outpatient services, the only tertiary care hospital in Suffolk County. Concurrently, we established a registry to monitor patient outcomes for all patients receiving CCTA at Stony Brook Medicine. Our registry contained nearly 15,000 patient CCTA procedures. Our major registry study established the effectiveness of CCTA as an imaging modality for evaluating ED chest pain in a cost efficient manner with a false negative rate less than 1% [5]. However, our registry reflects the poorer positive predictive values documented by other industry studies [6-8].

False positive workup results in the necessity of performing cardiac catheterization on patients at risk for obstructive disease based on assessment with current standard of care (combined screening with CCTA and stress MPI). Reduction in the rate of false positive testing would lead to reduction in risk from invasive procedures and radiation exposure to patients and reduced cost to the health care system.

Several medical institutions currently use HeartFlow CT-FFR as standard of care for evaluating obstructive disease. Generally, the standard of care at these institutions is to refer patients who are 30 to 100 percent obstructed by CCTA and who have reduction of flow \leq to 0.8 that is deemed to be medical significant by the attending cardiologist to Invasive FFR. HeartFlow has reported to us confidentially that this routine use of CT-FFR has resulted in a 54% reduction in false positive rate as compare to use of CCTA alone.

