6.1 General Design

This will be a prospective clinical trial designed to evaluate the incremental benefit of virtual FFR measured from CCTA, compared to invasive FFR and CCTA for the detection of flow-limiting coronary stenosis, as defined by invasive FFR ≤ 0.8 and vessel diameter of $\geq 2\text{mm}$.

572 consecutive patients who present to Lenox Hill Hospital Outpatient Clinics for CCTA due to chest pain or stable angina over a ten month period and meeting the study inclusion criteria are eligible for the study (Figure 1). Our team will employ CCTA-appropriateness criteria to ensure proper selection of patients, derived from the Appropriate Use Criteria for Cardiac Computed Tomography published in 2010 and jointly authored by multiple societies including ACCF, SCCT, and ACR [10]. FFR-CT measurements will be performed by a core laboratory in a blinded fashion. All eligible patients will undergo 64-slice or greater multi detector CCTA and CT-FFR measurements. The severity of the stenosis will be determined on site by level III CCTA readers. Patients with obstructive lesions of (30% to 100% stenosis) will receive Stress-MPI, per SOC protocol, and CT-FFR. Patients with positive Stress-MPI and CCTA (50% - 70%) or positive CCTA (71% to 100%) will undergo ICA with invasive FFR measurement in accordance to accepted guidelines and established practice standard. Those patients with invasively measured FFR ≤ 0.8 and with vessel diameter of $\geq 2\text{mm}$, or those who require revascularizations based on invasively estimated stenosis severity will be considered to have flow-limiting obstructive CAD, while the rest will be considered to have non-flow limiting obstructive CAD (if also $>50\%$ stenosis on ICA). If stenosis severity turns out to be $< 50\%$ after ICA (the gold standard), we will conclude that these patients have non-obstructive CAD. (Figure 1). Patients with 30% to 49% obstructive disease, according to CCTA, will be referred to optimal follow up care only. Any in this group who have positive CT-FFR will return for

ICA with invasive FFR measurement, and follow the protocol for those with 50% to 100% obstruction.

Figure 1:

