6.2 Primary Study Endpoints

Defining an event as performance of ICA when no intervention is necessary, we expect to compare event rates for patients treated with CCTA and FFR-CT, using t-tests and a multivariate, risk adjusted 90 day hazard model with 95% confidence interval. Our null hypothesis is that outcomes will not vary regardless of which testing is used to assess

obstructive disease. Our alternative hypothesis is that evaluation with FFR-CT as oppose to CCTA will change the event rate. We will also correlate noninvasive and invasive FFR studies.

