6.4 Primary Safety Endpoints

The study design evaluates the potential to substitute non-invasive for invasive FFR. Safety endpoints of the study include: 1. Evaluating the diagnostic accuracy of non-invasive FFR. If the end result demonstrates that the procedure is less accurate than invasive FFR, patients receiving this procedure, as an alternative to the current standard will be at greater risk. 2. Patients who undergo invasive procedures experience increased risk of infection or other comorbidities or complications, as compared to those who do not undergo invasive procedures. Therefore, if the noninvasive protocol results are not significantly different than the invasive results, patient safety might potentially be increased by using the noninvasive technology. 3. Noninvasive technology has the potential to reduce radiation exposure by reducing the number of invasive angiography and Stress MPI procedures necessary to complete patient evaluation. This increases patient safety relative to the adverse effects of radiation exposure.

7 Subject Selection and Withdrawal

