14.2 Statistical Methods

Statistical Aims

1. *To determine the sensitivity, specificity, positive predictive value (PPV) and negative predictive value (NPV) of the CCTA test (with or without stress MPI, as specified in Figure 1) + CT-FFR evaluation to identify chest pain patients with flow-limiting obstructive CAD. The ICA test will be used as gold standard.*
2. *To determine inter-observer reliability of CCTA and CCTA+CT-FFR test readings between an experienced and a non-experienced reader, and compare the results between CCTA and CCTA+CT-FFR; to determine the intra-observer reliability of CCTA and CCTA-FFR reading, for both the experienced and non-experienced reader, and for each reader compare the results between CCTA and CCTA+CT-FFR.*

3. To identify factors of return visit within 90 days in patients who had no ICA test or a negative ICA test result.

Outcome Variables

- *CCTA+CT-FFR test status (Positive/Negative). The test is deemed positive if ICA is required and negative if ICA is not required (see Figure 1).*
- *ICA (gold standard) test status (Positive / Negative). ICA is deemed positive if $FFR < 0.8$ and vessel diameter $>= 2\text{mm}$ or if the patient requires revascularizations based on invasively estimated stenosis severity. It is deemed negative otherwise.*
- *Return visit within 90 days (Y/N). Return visit is defined as patients who return for unplanned cardiac care, including emergency room visits, emergency hospital admissions, urgent percutaneous coronary intervention, coronary artery bypass graft, or acute myocardial infarction. Descriptive statistics (n, mean, median, standard deviation, IQR, frequencies and percentages) will be used to describe the demographic and clinical characteristics of the whole sample.*

For Aim 1, sensitivity, specificity, PPV, and NPV will be computed using the ICA result as the ‘true’ flow-limiting obstructive CAD status and the CCTA+CT-FFR test result as the ‘test’ status. Exact binomial 95% confidence intervals will be computed.

For Aim 2, inter- and intra-observer reliability for the CCTA and CCTA+CT-FFR tests will be assessed using Cohen’s Kappa coefficient. Dependent Kappa coefficients will be compared using a method developed by Donner et al .

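### Section 14.2 has no analysis comparing CT-FFR with invasive FFR, and the correlation mentioned in section 6.2 would not show bias at the 0.8 cut

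*Combined protocol and SAP*

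**What the plan says.** Section 6.2 (Primary Study Endpoints) ends with "We will also correlate noninvasive and invasive FFR studies". It names no coefficient, no unit of analysis (vessel or patient) and no estimate of bias.

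Section 6.4 (Primary Safety Endpoints) gives the purpose: "The study design evaluates the potential to substitute non-invasive for invasive FFR". Its first listed safety endpoint is the diagnostic accuracy of non-invasive FFR, with no method attached.

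Section 14.2 has two analyses that come near the question:

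- Aim 1 reports sensitivity, specificity, PPV and NPV against ICA with exact intervals. Its test variable is the whole pathway: "The test is deemed positive if ICA is required and negative if ICA is not required".
- Aim 2 uses Cohen's kappa, but for readers: "inter- and intra-observer reliability for the CCTA and CCTA+CT-FFR tests will be assessed using" that statistic.

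The cut is not settled. Section 6.1 describes flow-limiting stenosis "as defined by invasive FFR ≤ 0.8 and vessel diameter of" at least 2 mm. In section 14.2, "ICA is deemed positive if $FFR < 0.8$ and vessel diameter" is at least 2 mm. The only numeric CT-FFR cut is in section 3.4, as practice at other institutions: a reading less than or equal "to 0.8 that is deemed to be medical significant by the attending cardiologist".

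**The concern.** Replacing one measurement by another at a fixed threshold is a question of agreement. A correlation coefficient measures how closely paired values follow a straight line, whatever its intercept and (positive) slope. If CT-FFR read consistently low or high, r would not change, but patients near 0.8 would move across the cut.

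The coefficient also depends on the spread of FFR among the patients measured. Invasive FFR exists only for those sent to ICA, partly because CT-FFR was positive (sections 6.1 and 8.3). A low r could therefore come from a narrow range despite good agreement, and a high r from a wide range despite poor agreement.

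At stake is the trial's evidence on the substitution question in section 6.4. Without a stated agreement analysis, the report could give a coefficient and leave bias and misclassification at the cut unexamined.

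**Working it through.** **1. Is there a plan figure to reproduce?** Not for this comparison: the documents give no sample size or precision for it. The figure in section 14.1 concerns the false-positive rate (14% to 6%, two-sided 0.05, 80% power) and reproduces:

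- n = [(1.960·√(0.14·0.86) + 0.842·√(0.06·0.94)) / 0.08]² = 120.99, so 121.
- 121 / (0.60·0.35) = 576.2, against 576 stated.

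The CT-FFR versus invasive FFR comparison does not enter this calculation.

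**2. Does Aim 1 fill the gap?** Under section 8.3, a CT-FFR-negative patient in the highest stenosis band, or with 50-70% stenosis and a positive stress MPI, goes to catheterization. Because ICA is then required, Aim 1 counts that patient as test-positive. Aim 1 evaluates the pathway and does not isolate CT-FFR.

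**3. Constant offset without random error.** Let CT-FFR = invasive FFR − 0.05. Then r = 1.00. With CT-FFR positive at or below 0.80, everyone with invasive FFR between 0.80 and 0.85 is wrongly positive. The offset, the Normal shape and the SDs are assumptions, since the documents give none. Two assumptions about the centre give the range.

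(a) Mean 0.80. Share = Φ(0.05/SD) − 0.5.

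(b) 14% of patients above 0.80, approximating the planning rate of negative ICA in section 14.1. The mean is then 0.80 − 1.080·SD, and share = 0.14 − [1 − Φ(1.080 + 0.05/SD)].

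| SD | (a) mean 0.80 | (b) 14% above 0.80 |
|---|---|---|
| 0.08 | 23.4% | 9.6% |
| 0.10 | 19.1% | 8.3% |
| 0.12 | 16.2% | 7.3% |

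Case (a) puts half of catheterized patients above 0.80, which sits poorly with 14%. Case (b) is only approximate, because section 14.2 also allows a positive ICA through revascularization on stenosis severity, so 14% is not strictly the share with FFR above 0.80.

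**4. Offset with random error.** Assume mean 0.80, SD 0.10 and error SD 0.07. Then r = 0.10/√(0.10² + 0.07²) = 0.819 at every offset. A simulation of 2,000,000 pairs gave:

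| Offset | r | Sensitivity at 0.8 | Specificity at 0.8 |
|---|---|---|---|
| 0 | 0.819 | 0.81 | 0.81 |
| −0.05 | 0.819 | 0.93 | 0.61 |
| +0.05 | 0.819 | 0.61 | 0.93 |

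Two other assumed settings (mean 0.82, SD 0.10, error SD 0.07; mean 0.78, SD 0.12, error SD 0.08) showed the same pattern, with r fixed at 0.819 and 0.832. The mean difference moves one-for-one with the offset.

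**5. Is an agreement analysis feasible?** Take 121 pairs, one per patient, as a best case, and assume a difference SD of 0.05 to 0.10.

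- Half-width of the 95% CI for mean bias: 1.980·SD/√121 = 0.009 to 0.018.
- Half-width for each limit of agreement: 1.96·SD·√(1/121 + 1.96²/(2·120)) = 0.015 to 0.031.

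This is useful precision without more patients, provided most ICA patients have paired values.

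**The case against.** The strongest reply is that the plan never names a correlation coefficient. The protocol uses the verb loosely: in section 2, invasive FFR and 90-day outcomes "will be correlated with each diagnostic modality in order to evaluate positive and negative predictive value", and section 3.1 gives nearly the same sentence with a different verb. Section 2 also speaks of correlating readers' results, which section 14.2 then analyses with kappa. A reader might infer that the sponsor has chosen a wrong method and means to prove interchangeability with r. The documents do not support that. What stands is that the analysis is unspecified, and that its natural reading would not answer section 6.4.

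A second reply is that accuracy is already covered, by the first safety endpoint and by Aim 1. This is partly right: the plan does link substitution to accuracy, and Aim 1 is similar in kind to the 2x2 table proposed here. But the endpoint has no method, and Aim 1 does not isolate CT-FFR.

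Third, under section 8.3 a positive CT-FFR leads to catheterization with invasive FFR, so CT-FFR does not replace invasive FFR in those patients during the trial. That is so. The concern is what the trial can later say about substitution.

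Fourth, limits of agreement and a 2x2 table come from the same selected patients as r. This also stands: they show bias and misclassification in that group but do not remove the selection.

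**Conclusion.** The point holds as a minor one. Section 14.2 lacks an analysis of CT-FFR against invasive FFR that fits the question in section 6.4, and the one sentence in section 6.2 does not supply it. That a correlation coefficient is blind to a constant offset or positive rescaling is mathematical and needs no assumption. That a coefficient is intended is an inference.

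The size is illustrative: about 7-10% to 16-23% of catheterized patients wrongly positive under an assumed −0.05 offset, depending mainly on where invasive FFR is centred. A reader might take the upper figures as the expected error. They depend on a mean of exactly 0.80, and neither that mean nor the offset comes from the documents.

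Nor should a reader infer that the main result is at risk. The sentence is an addition to the primary endpoint. The event-rate comparison and the figures of 121 with ICA and 576 completers do not depend on it.

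**What to change.** In section 14.2, add:

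1. The mean of CT-FFR minus invasive FFR with 95% limits of agreement (Bland-Altman), allowing for clustering by patient if several vessels are used.
2. The 2x2 classification of CT-FFR against invasive FFR, with exact confidence intervals if there is one pair per patient and cluster-adjusted intervals otherwise.
3. Any correlation coefficient as descriptive only, with section 6.2 reworded to match.

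Before the 2x2 table can be run, reconcile the invasive cut between sections 6.1 and 14.2, which differ at exactly 0.80, and state the CT-FFR cut this study uses. State also the unit of analysis, and that results apply only to patients sent to ICA who have paired FFR values. Patients classed positive through revascularization on stenosis severity may have no invasive FFR value.

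The cost is small: paired values must be recorded on the case report form, which the documents do not say is planned, and there is a little more analysis. No added patients or procedures are needed.

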6.3 Secondary Study Endpoints

We will assess inter-observer reliability of the two reader cohorts' (> 10 years experience and less than 10 years experience) readings for CCTA and CT-FFR.. We will also assess the nondiagnostic rate for CT-FFR exams as compared to independent quality ratings of CCTA scans by the scan reader. Scans will be rated as excellent, good, adequate, or non-diagnostic. Non-diagnostic exams will not be sent to CT-FFR. For those sent to CT-FFR we will compare the percentage of non-diagnostic exams to the percentage of non-diagnostic for CT-FFR, and we will also correlate exam results by level of obstruction.

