7.6 Early Withdrawal of Subjects

7.6.1 When and How to Withdraw Subjects

Subjects may withdraw from the study for any reason at their request. Subjects who cannot or will not cooperate with the CCTA technologists instructions will be withdrawn from the study, because we will not be able to perform a CCTA. For some subjects, FFR results may not be available due to poor quality of CCTA scan. In this case, the subject will remain in the study, following standard of care, but no FFR reading will be available. If at any time a patient experiences an adverse reaction to medical care, the procedure will be ended and the patient will be withdrawn from the procedural part of the study. Wherever possible, when patients withdraw from the procedure part of the study (the CCTA) we will make every effort to conduct study follow-up.

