8.3 Method for Assigning Subjects to Treatment Groups

This is not a randomized study. Treatment assignments will follow the clinical protocol.

Once the CCTA results are interpreted by the physician, the physician will order CT-FFR exams for patients whose level of stenosis by CCTA standards is 30% to 100%.

If CT-FFR is positive patients will be referred for Cardiac Catheterization and invasive FFR.

If CT-FFR is negative, and level of obstruction is 30 to 49% by CCTA standards, patients will be referred to optimal medical care.

If CT-FFR is negative and level of obstruction is 50% to 70% by CCTA standards, patient will be referred for stress MPI. If stress MPI is positive patients will be referred for Cardiac Cath and invasive FFR. If stress MPI is negative, patients will be referred to optimal medical care.

If the patient has had a stress MPI within one year of the CCTA exam and the CCTA exam result is 50% to 70% obstructive, the physician will rely on the prior stress testing result, rather than repeating the stress test. If the stress testing results was negative, the patient will be referred to optimal medical care. If, in the investigator's opinion, the results indicate that the patient is at increased risk of obstructive disease, when considered with the CCTA findings, the patient will be referred to Cardiac Cath and Invasive FFR.

If CT-FFR is negative and level of obstruction is 70% to 100% by CCTA standard, patient will be referred to Cardiac Cath and Invasive FFR.

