14.1 Sample Size Determination

Based on data from Stony Brook and confidential data HeartFlow reported from providers who have been using CT-FFR in a similar manner as we propose for this study, we estimated that about 60% of stable chest pain patients who had CCTA were diagnosed with coronary stenosis of 30% to 90% and received CT-FFR. Of these patients, about 35% had an ICA test, and 14% of those had a negative ICA test result (i.e. the false-positive rate of CCTA+CT-FFR was 14%). A sample of 121 patients who received ICA will yield 80% statistical power of detecting a 60% reduction in the false-positive rate (from 14% to 6%), based on a two-sided one sample Chi-square test with 0.05 significance level. Assuming a similar prevalence of flow-limiting obstructive CAD and assuming that similar proportions of stable chest pain patients who had CCTA will receive CCT-FFR and then ICA, 576 stable chest pain patients who had CCTA need to be complete the clinical trial. In order to target 576 subjects completing the trial, we estimate that number of patients, it will be necessary to 594, because 18 patients who enrolled were screen failures.

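### Section 6.3 keeps non-diagnostic CCTA scans out of CT-FFR and then compares non-diagnostic percentages among the scans sent, so the CCTA side is 0% by construction

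*Combined protocol and SAP*

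**What the plan says.** Section 6.3 sets out a secondary endpoint in four steps.

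- The aim: "We will also assess the nondiagnostic rate for CT-FFR exams as compared to independent quality ratings of CCTA scans by the scan reader".
- The scale: "Scans will be rated as excellent, good, adequate, or non-diagnostic".
- The sending rule: "Non-diagnostic exams will not be sent to CT-FFR".
- The comparison: "For those sent to CT-FFR we will compare the percentage of non-diagnostic exams to the percentage of non-diagnostic for CT-FFR".

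Other sections bear on it.

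- Section 2 provides for two readers: "Each CCTA will be read by a less experienced and a more experienced reader". No section says whose quality rating decides whether a scan is sent.
- Section 8.3 states the sending rule by stenosis only: "the physician will order CT-FFR exams for patients whose level of stenosis by CCTA standards is 30% to 100" per cent. Sections 8.4 and 9 do the same, so the quality exclusion appears only in 6.3.
- Section 7.6.1 recognises that CT-FFR can fail: "FFR results may not be available due to poor quality of CCTA scan".
- Section 14.2 gives aims, outcome variables and methods for diagnostic accuracy, reader reliability and return visits, but none for non-diagnostic rates. Section 14.3 says only that all enrolled subjects are analysed, with suitable adjustment for those who do not complete a part.

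**The concern.** The stated aim is sensible: find out how often CT-FFR fails and how that relates to the quality of the underlying scan. The comparison sentence does not deliver it. It restricts attention to scans that have already passed the CCTA quality check, and then uses failure of that same check as the comparator. One side of the comparison is fixed by the sending rule before any data are seen.

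The study could then report that CT-FFR is non-diagnostic more often than CCTA when no other direction was possible. Meanwhile the informative question, how CT-FFR failure varies across the excellent, good and adequate grades, has no planned analysis.

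**Working it through.** **Scans sent.** Section 14.1 requires 121 ICA patients and assumes that 60% of CCTA patients receive CT-FFR and 35% of those have ICA. The plan's total reproduces: 121 / (0.60 × 0.35) = 576.2, against its 576. Scans sent are then about 0.60 × 576 = 345.6, or 346. This is approximate, because the source figure is "about 60% of stable chest pain patients who had CCTA were diagnosed with coronary stenosis of 30% to 90% and received CT-FFR", whereas Section 8.3 sends scans up to 100% stenosis. The logic below does not depend on it.

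**Assumptions.** The plan gives no non-diagnostic rate for either method and names no test. All rates below are assumed.

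**Reading 1: as written, both percentages among scans sent.** Let q be the CT-FFR non-diagnostic proportion. No scan sent was rated non-diagnostic by the reader who decides sending, so the CCTA proportion is 0/346 and

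CT-FFR minus CCTA = q − 0 = q ≥ 0.

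| Assumed q | CT-FFR failures | Exact 95% CI | CCTA | Difference (points) |
|---|---|---|---|---|
| 0% | 0/346 | 0 to 1.1% | 0/346 | 0 |
| 2% | 7/346 | 0.8 to 4.1% | 0/346 | +2.0 |
| 5% | 17/346 | 2.9 to 7.8% | 0/346 | +4.9 |
| 10% | 35/346 | 7.2 to 13.8% | 0/346 | +10.1 |

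If an exact paired (McNemar) test were applied, every discordant pair would fall on the same side, so with x CT-FFR failures the two-sided p-value is 2 × 0.5^x. For x = 5 (1.4%), p = 0.0625. For x = 6 (1.7%), p = 0.031. Six failures in 346 would count as significant against CT-FFR, and no result could favour it.

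**Reading 2: CCTA over all scans, CT-FFR over scans sent.** Let c be the CCTA non-diagnostic proportion over all 576. Assumed values near 2%, 5% and 10% give 12/576 (exact 95% CI 1.1 to 3.6%), 29/576 (3.4 to 7.2%) and 58/576 (7.7 to 12.8%). With q and c each between 2% and 10%, q − c runs from 2 − 10 = −8 to 10 − 2 = +8 points. Either sign is possible. But the denominators differ, and the worst scans have been removed from the CT-FFR side only, which favours CT-FFR.

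**Reading 3: one reader decides sending, the other supplies the comparator.** The CCTA percentage could then exceed 0%, but it would measure disagreement between readers about scans the first had passed. Section 6.3 refers to a single scan reader and does not describe this.

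**Power of a trend across grades.** Assume a 40/40/20 split of the 346 scans, that is 138/138/70 excellent, good and adequate, and a Cochran-Armitage test at two-sided 0.05 (20,000 simulations).

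- Failure rates 2/5/12%: expected failures 138 × 0.02 + 138 × 0.05 + 70 × 0.12 = 18.1; power about 84%.
- Failure rates 3/5/8%: expected failures 138 × 0.03 + 138 × 0.05 + 70 × 0.08 = 16.6; power about 36%.

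**The case against.** The strongest reply is that the difference under the literal reading is not meaningless. It equals the CT-FFR failure rate among scans already judged readable, which is the extra non-diagnostic burden of adding CT-FFR after an acceptable CCTA. Section 6.3 states no hypothesis or superiority claim, so talk of a tie supplies a contest the plan does not formally set up. This stands in part. The CT-FFR rate is informative and should be reported. But it is informative as a single proportion; setting it against a fixed zero adds nothing, and the section does say that the two percentages will be compared.

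A second reply is that the 0% is conditional. With two readers per scan and none named, the other reader's rating could give a non-zero figure, and the quality exclusion rests on one sentence that Sections 8.3, 8.4 and 9 do not repeat. This is correct, and it is why the 0% is claimed only for the reader whose rating decides sending. It shows a further gap and does not rescue the sentence.

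A third is that the sponsor probably meant the all-scan CCTA rate, with some support from Section 14.3. That may be so, but 6.3 limits the comparison to scans sent, and the all-scan reading brings unequal denominators.

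Finally, this is one secondary endpoint with no power calculation, and the rates can be recomputed at reporting. That limits its importance, but does not justify leaving the denominator to be chosen after the data are seen.

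**Conclusion.** The concern holds. Under the wording of Section 6.3, the CCTA non-diagnostic percentage among scans sent is 0% for the reader whose rating decides sending. The difference therefore equals the CT-FFR failure rate and cannot be negative. This follows from the text alone. The illustrated size, 0 to +10 points on about 346 scans, rests on assumed failure rates and on the 60% in Section 14.1. Under the all-scan reading the sign is open, and the −8 to +8 point range simply reflects the assumed 2% to 10% for each rate. Nothing in Sections 14.2 or 14.3 chooses between the readings. The effect is confined to this secondary endpoint, so the change should be made but does not bear on the main result.

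**What to change.** Replace the comparison sentence in Section 6.3 with two statements.

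1. Report the CCTA non-diagnostic rate over all CCTA scans read, and the CT-FFR non-evaluable rate over all scans submitted, each with an exact 95% CI and without a head-to-head comparison.
2. Among scans sent, report the CT-FFR non-evaluable rate by CCTA quality grade (excellent, good, adequate) with 95% CIs, and a trend test as support.

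Name the reader whose quality rating decides sending and is used in the table. Add the method to Section 14.2. The number of scans not sent for quality can be given as a separate count; patients whose stenosis could not be determined should not be counted as CT-FFR failures. Sections 8.3, 8.4 and 9 should be reconciled with 6.3 on whether scan quality forms part of the sending rule.

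The cost is small: one rewritten sentence, a short method entry, one table and a consistency check across sections, with no new data or patients. What is given up is a direct comparison of the two percentages. The trend test may be weak, so the confidence intervals by grade should lead.
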